16.0 SPECIAL NOTES

16.1 Informed Consent

A written consent form will be obtained from each subject and filed by the Investigator with the subject's records, in accordance with 21 CFR Part 50.

16.2 Alteration of the Study

Neither the Investigator, nor the Sponsor, will modify or alter this protocol without first obtaining the concurrence of the other parties. All protocol modifications including, but not limited to changes in the Principal Investigator, inclusion/exclusion criteria, number of subjects to be enrolled, study sites, or procedures must be submitted to the GIRB as a written amendment for review and approval prior to implementation, with one exception: when necessary to eliminate an apparent immediate hazard to the subject.

16.3 Protocol Deviations

This study will be conducted as described in this protocol, except for an emergency situation in which the protection, safety, and well-being of the subject requires immediate interventions, based on the judgment of the Investigator. In the event of a significant deviation from the protocol due to an emergency, accident, or mistake, the Investigator or designee will document the details of the situation and any subsequent decisions. All deviations from the protocol or approved amendments shall be documented by BioScience Laboratories, Inc. Any deviation to the protocol that may have an effect on the safety or rights of the subjects will be reported immediately to the local GIRB and Sponsor representative.

16.4 Quality Assurance Audits

The BioScience Laboratories, Inc. Quality Assurance Unit (QAU) will conduct in-phase audits of critical testing processes at least once during testing and will advise the Principal Investigator and Management of the outcomes of these audits. On completion of testing, the QAU will perform an audit of the data and of the Final Report in its entirety.

17.0 FINAL REPORT

The final report will be generated and will summarize the method, data, and conclusions relative to the test materials and the subjects. The statistical analysis used in the report will be provided by BD. Copies of the data will be incorporated into the report.

APPROVAL OF PROTOCOL AMENDMENTS 18.0

No changes may be implemented to any aspects of this protocol until written approval has been obtained from the Sponsor and the GIRB (if needed) with one exception: when necessary to eliminate an apparent immediate hazard to the subject.

20.2 Source Document Maintenance

Source documents are defined as the results of original observations and activities of a clinical investigation. Source documents will include, but are not limited to study progress notes, computer printouts, screening logs, laboratory notebooks and recorded data from automated instruments. All source documents produced in this study will be maintained by the Investigator and made available for inspection by authorized persons. The case report forms (CRFs) will be the primary source documents for the study. All data will be directly recorded on the CRFs. The original signed informed consent form

from each participating subject will be filed in the Study File and a copy given to the subject.

20.3 File Management at the Study Site

The Investigator will not dispose of any records relevant to this study without written permission from the Sponsor and providing an opportunity for the Sponsor to collect such records. The Investigator shall take responsibility for maintaining adequate and accurate hard-copy source documents of all observations and data generated during this study including but not limited to the essential documents noted below in Section 20.4. Such documentation is subject to inspection by the Sponsor, the FDA, or any applicable regulatory agency. If the Investigator is not able to store the records, he or she will contact the Sponsor and make arrangements for the Sponsor to assume the responsibility for the continued storage.

20.4 Study File Management

It will be the responsibility of the Investigator to assure that the Study File is maintained. The Study File for this protocol will contain, but will not be limited to, the information listed below:

- Investigational Brochure or other appropriate product safety information
- Signed Protocol
- Revised Protocol (if applicable)
- IRB-Approved Informed Consent Form (blank)
- Copy of Signed Form(s) FDA-1572 (if applicable)
- Financial Disclosure for the Investigator and Subinvestigator (if applicable)
- Curriculum Vitae of Investigator and Subinvestigator (if applicable)
- DHHS Number for IRB, or other documentation of IRB compliance with FDA regulation
- Documentation of IRB approval of protocol, consent form, any protocol amendments and any consent form revisions
- All correspondence between the Investigator, IRB, and Sponsor relating to study conduct
- Copies of information related to SAE and the information on Immediately Reported Adverse Events
- Copy of completed Initiation Report provided to IRB
- Research Site Signature Log
- FDA's Clinical Investigator Information Sheets (if applicable)
 BSLI PROTOCOL #1608374-103 / BD PROTOCOL MPS-16IPVAW01

- CRA Monitoring Log (if applicable)
- Drug Invoices and Accountability Records
- Study specific training records for investigation site personnel, including Site Signature Delegation Logs
- Enrollment/Disposition log showing subjects screened, enrolled, disqualified, withdrawn, and completed
- Sample Submission Form, Product Receipt Logs and Product Tracking Forms

[figure not shown]
To protect privacy and maintain the confidentiality of data, subjects will be assigned a unique study number, all study samples and research records will be identified using the subject's study number, and electronic databases will be kept on password-protected computers.

21.0 LIABILITY AND INDEMNIFICATION

Test Facility's liability to Sponsor under this Protocol shall be limited to the price of this evaluation. Sponsor shall be responsible to Study Participants (when applicable) and to other third parties for the fitness of the product for use as defined in the Study Protocol.

23.0 PROTOCOL ACCEPTANCE

ACCEPTED BY: BIOSCIENCE LABORATORIES, INC. (TESTING FACILITY) [name] [name]

O Numbering incorrect. Acceptance is section 22.0. @ [name] 09/14/16

APPENDIX 1

PRODUCT APPLICATION INSTRUCTIONS

For all Test Materials: Investigational Product, Vehicle Control, and Active Control

- 1) Weigh the unopened cloth package and record weight.
- 2) Open package and remove a single cloth from the package (for Sage cloth: according to the manufacturer's instructions).
- 3) Follow application instructions as noted below.
- 4) Following treatment application, weigh the used cloth test material with the package (including unused cloth) and record the weight.
- 5) Retain the label from the package and discard both the used and unused cloths.

Treatment Site Application Instructions

Abdominal Test Site (5in. x 5in.)

[figure not shown]
- 1) Using a single cloth for each anatomical region, vigorously scrub skin back-and-forth for three (3) minutes completely wetting the treatment area.
- 2) At the completion of the three (3) minute application, allow the area to air dry for one (1) minute prior to the initiation of the sampling times.

Inguinal Test Site (2in. x 5in.)

[figure not shown]
- 1) Using a single cloth for each anatomical region, vigorously scrub skin back-and-forth for three (3) minutes completely wetting the treatment area.
- 2) At the completion of the three (3) minute application, allow the area to air dry for one (1) minute prior to the initiation of the contact times.

APPENDIX 2

ANATOMICAL DIAGRAM OF THE SAMPLING SITES

ABDOMINAL TEST SITES

BSLI PROTOCOL #1608374-103 / BD PROTOCOL MPS-16IPVAW01 Page 37 of 46

APPENDIX 3

VALIDATION OF NEUTRALIZATION EFFECTIVENESS: **CLINICAL TRIAL EVALUATION**

1.0 PURPOSE OF NEUTRALIZER EFFECTIVENESS STUDY

The purpose of this neutralization study is to assure that the neutralizers used in the recovery medium quench the antimicrobial activity of the test materials, and are not toxic to the bacteria. The study will comprise both an *In-Vivo* component performed using human subjects, and an *In-Vitro* component performed based on ASTM E1054-08(2013), Standard Test Methods for Evaluation of Inactivators of Antimicrobial Agents. Staphylococcus epidermidis MRSE (ATCC #51625) and Staphylococcus epidermidis (ATCC #12228) will be used as the challenge species in both (*In-vitro and In-vivo*) components of the neutralizer validation study.

2.0 SCOPE

An effective nontoxic method of neutralization must be employed to eliminate the antimicrobial activity of a test material quickly. Sufficient supporting data are required to show that the neutralizing method employed is effective. A known population of microorganism must be exposed to the antimicrobial test materials, diluent/recovery media, the neutralizing solution, and the neutralizing solution plus antimicrobial test material in order to determine whether microbial inhibition is present.

Neutralizing methods include chemical inactivation, dilution of antimicrobial test material to a sub-inhibitory concentration, and membrane filtration. The procedures detailed here deal with chemical inactivation and dilution of antimicrobial test material, as well as recovery from human subjects.

The *In-Vivo* component of the neutralization study will use the Investigational Product and Active Control. At least eight human subjects will be tested using product applications on the skin of the abdomen, to obtain a minimum of four samples per test material challenged with each challenge species.

3.0 **TEST MATERIALS**

The Investigational Product and Active Control to be used in this open label evaluation will be supplied by the Sponsor (BD). Responsibility for the identity, strength, purity, composition, and stability of the Sponsor-provided test materials used in testing rests with the Sponsor. The test materials will be received and stored by BioScience Laboratories, Inc. (BSLI) in accordance with instructions from the Sponsor and retained in secure quarantine when not being used in testing. BSLI will maintain an inventory of the test materials in secure quarantine and a log of use. Unused, sealed test materials will be stored by BSLI until the Sponsor specifies its disposition. In the absence of a disposition request from the Sponsor within 1 year of planned usage, the test materials

will be returned to the Sponsor. No test materials will be destroyed unless so requested by the Sponsor. Complete product information will be presented in the Final Report, if provided by the Sponsor.

Investigational Product: Thermally treated polyester A&W5 Cloths Impregnated

with 0.4% w/v Octenidine Dihydrochloride (OCT)

Aqueous Solution

Active Ingredients: 0.4% w/ v Octenidine Dihydrochloride (OCT) Aqueous

Solution

Lot Number: **Expiration Date:**

Sage 2% Chlorhexidine Gluconate Cloth Active Control:

Active Ingredients: 2% Chlorhexidine Gluconate (CHG)

Lot Number: Expiration Date:

4.0 LABORATORY EQUIPMENT, SUPPLIES AND MEDIA

4.1 Equipment

The equipment used during this neutralization will be detailed on Clinical Trials Equipment Tracking Form(s), and the form(s) will be included in the Final Report.

4.2 **Supplies**

The supplies used during this neutralization will be detailed on Supplies Tracking Form(s) and the form(s) will be included in the Final Report.

4.3 Test Media

Sampling Solution

Sterile Sampling Solution (SS)

Diluting Fluid

Butterfield's Phosphate Buffer Solution (PBW)

Media

Tryptic Soy Agar with product neutralizers (TSA+)

Tryptic Soy Agar with 5 g Polysorbate 80 and 0.7 g Lecithin added to 1.0 L deionized water.

Tryptic Soy Agar (TSA)

Tryptic Soy Broth (TSB)

Phosphate Buffered Saline (PBS)

5.0 SUBJECT SELECTION

5.1 **Number of Subjects**

A sufficient number of overtly healthy subjects at least 18 years of age will be admitted into the study to ensure collection of at least four samples for each of the two test materials and each challenge species (eight subjects).

5.2 **Subject Recruitment**

Subjects must meet the inclusion and exclusion criteria in Sections 11.3 and 11.4 of the protocol to which this neutralizer validation is attached, except for the baseline bacterial count, the 72-hour exclusion from showering/bathing criteria, and the length of the washout period. The neutralization subjects do not require a minimum baseline count and they only need to avoid topical and systemic antimicrobials for 7 days (not 14 days) prior to Test Day. Subjects will be asked to provide information on demographics and inclusion/exclusion criteria and sign the Informed Consent and Authorization Forms including Authorization to Use and Disclose Protected Health Information Form, and List of Restricted Products before beginning the 7-day washout period (subjects will be provided with a product restriction kit). When subjects return to begin their participation in the study they will again be asked to provide information relative to inclusion/exclusion criteria. If they meet all inclusion/exclusion criteria, they may be enrolled. These subjects will be identified by the letter "N" for neutralization and a subject number starting with 001.

Each subject will receive both of the two test materials, one assigned to one side of the abdomen and the other assigned to the other side.

PROCEDURES 6.0

6.1 Compliance with Good Clinical Practices and Regulatory Requirements

The study will be conducted in compliance with the Good Clinical Practice regulations as required by the FDA, Good Laboratory Practice regulations as required by the FDA, the standard operating procedures of BioScience Laboratories, Inc., the study protocol, and any protocol amendments, and the regulatory requirements of the FDA and ICH.

Subjects will be questioned prior to and during the study to ensure compliance with study requirements.

6.2 **Product-Restriction Period**

The 7-day period prior to the neutralization will be designated the "product-restriction" period. During this time, subjects will avoid the use of medicated soaps, lotions, shampoos, deodorants (with exception of deodorant provided in the product-restriction kit), etc., as well as skin contact with solvents, acids, and bases. Subjects will also avoid sunbathing, using UV tanning beds or bathing in biocide-treated (e.g., chlorinated) pools and/or hot tubs. Subjects will be provided a kit containing products that they will be instructed to use exclusively for personal hygiene during the course of the study.

Subjects must not remove hair from the anatomical sites to be treated from the beginning of the product restriction period until after the neutralization has been completed.

During the Product-Restriction Period (at least 72 hours prior to the test period), the subjects will be examined physically to ensure that there is no evidence of injury, dermatosis, or dermatitis present at the sampling sites (abdomen), and hair on sampling sites will be clipped, if needed.

6.3 Randomization

The two test materials (Investigational Product and Active Control) will be assigned randomly to test sites per a computer-generated randomization schedule, such that each subject receives both of the test materials at the abdominal sites.

The challenge species will not be randomly assigned to a subject. Each challenge species will be tested separately and a group of four subjects will provide the samples for each challenge species.

6.4 **Test Inoculum Preparation**

Two days prior to beginning the neutralization assay, Staphylococcus epidermidis MRSE (ATCC #51625) or Staphylococcus epidermidis (ATCC #12228) from a stock culture slant, lyophilized vial, or cryogenic stock culture will be transferred into a tube containing Tryptic Soy Broth (TSB). The tube will be incubated for 24 hours \pm 4 hours at 30 °C \pm 2 °C.

One day prior to beginning the neutralization assay, loopfuls of the broth culture will be streaked onto Tryptic Soy Agar (TSA) plates, and the plates will be incubated for 24 hours \pm 4 hours at 30 °C \pm 2 °C.

Immediately prior to initiating the neutralization assay, an inoculum suspension will be prepared in Phosphate Buffer Saline (PBS) solution from the culture on an agar plate, and the concentration adjusted to approximately 3.0×10^8 to 1.0×10^9 CFU/mL. The suspension will then be serially diluted in PBS to achieve an inoculum titer of approximately 3.0×10^3 to 1.0×10^4 CFU/mL, and used as test inoculum. The below procedures will be performed with both microorganisms.

6.5 Inoculum Assay (Initial population) – Test C

Test Inoculum will be assayed by adding a 0.1 mL aliquot of the inoculum to 5.0 mL of PBS solution (IP), vortexing for at least 3 seconds, and immediately (within 1 minute) pour-plating, in duplicate, 1 mL aliquots of the IP with TSA. This assay will be performed three additional times for a total of four replicates.

The diluted test inoculum suspensions will be allowed to stand for at least 30 minutes, following which, 1 mL aliquots will be pour-plated, in duplicate, with TSA.

6.6 Product Efficacy Evaluation (In Vitro) – Test D

This phase of the neutralization assay determines whether the antimicrobial test material is able to reduce the population of the challenge microorganism. This assay will be performed in four replicates.

To each of four test tubes containing 5.0 mL of each Test Material, a 0.1 mL aliquot of the test inoculum will be added. The suspensions will be vortexed for at least 3 seconds and, immediately (within 1 minute), 1 mL aliquots of each replicate will be pour-plated, in duplicate, with TSA.

The tubes will be allowed to stand for at least 30 minutes, following which 1 mL aliquots of each replicate will be pour-plated, in duplicate, with TSA.

6.7 Neutralizing/Recovery Medium Inhibition Evaluations (In Vitro) – Test B

This phase of the neutralization assay assures that the sterile Sampling Solution (SS), the sampling solution employed in the evaluation, are not inherently toxic to the microorganisms. This assay will be performed in four replicates.

To each of four test tubes containing 5.0 mL of the sampling solution, a 0.1 mL aliquot of the test inoculum will be added. The suspensions will be vortexed for at least 3 seconds and, immediately (within 1 minute), 1 mL aliquots of each replicate will be pour-plated, in duplicate, with Tryptic Soy Agar with product neutralizers (TSA+).

The tubes will be allowed to stand for at least 30 minutes, following which 1 mL aliquots of each replicate will be pour-plated, in duplicate, with TSA+.

6.8 Diluent Broth Inhibition Evaluation (In Vitro) – Test B

This phase of the neutralization assay assures that the Butterfield's Phosphate Buffer Solution (PBW) employed in the evaluation is not inherently toxic to the microorganism. This assay will be performed in four replicates.

Four test tubes containing 5.0 mL of diluent broth to be used in the test will be prepared, and a 0.1 mL aliquot of the test inoculum will be transferred to each tube. The suspension will be vortexed for at least 3 seconds, and immediately (within 1 minute). 1 mL aliquots of each replicate will be pour-plated, in duplicate, with TSA+.

The tubes will be allowed to stand for at least 30 minutes, following which, 1 mL aliquots of each replicate will be pour-plated, in duplicate, with TSA+.

[figure not shown]
6.9 Neutralizer Efficacy Evaluation (In Vivo) – Test A

This phase of the evaluation determines whether the neutralizing method chosen effectively eliminates the antimicrobial activity of the test materials contained in the applicators.

Prior to sampling, the subjects will be questioned regarding adherence to the protocol. Subjects will also be examined physically to ensure no evidence of injury, dermatosis, or dermatitis is present at the sampling sites. Female subjects will be required to provide a urine sample for a pregnancy test. Only those female subjects with a negative test will be allowed to proceed into testing.

A 2" x 5" test area will be demarcated on each side of the abdomen. After the test areas are marked, each area will be processed using three 70% isopropyl alcohol swabs for a total of \sim 90 seconds (\sim 30 seconds each), followed by an air-dry for at least 1 minute. This step will prepare the skin for the neutralization test.

Neutralization Test Sites Diagram

A test material (reference Section 3.0 of the Validation of Neutralizer Effectiveness) will be applied to a 2" x 5" site on the abdomen of the subjects following the instructions for inguinal application in Appendix 1, with the randomly assigned test material.

The site will then be sampled using the Cylinder Sampling (Scrub Cup) Technique $10 \text{ minutes} \pm 30 \text{ seconds post product-application completion.}$

The Cylinder Sampling (Scrub Cup) Technique will be performed as described in Section 13.7 of the Study Protocol (using SS).

The volume of sample will be adjusted to 5.0 mL, inoculated with 0.1 mL of the test inoculum, and vortexed for at least 3 seconds. Immediately (within approximately 1 minute), 1 mL aliquots will be pour-plated, in duplicate, with TSA+.

The tube containing the sample and inocula will be allowed to stand for at least 30 minutes. Following the exposure, 1 mL aliquots of each sample will be pour-plated, in duplicate, with TSA+.

The process will be repeated on the remaining abdominal site with the randomly assigned test material. A total of 8 subjects will be treated with each of the two test materials (samples from four subjects used for one microorganism, samples from the remaining four subjects used for the remaining microorganism).

Following all sampling, each test site will be cleaned using a paper towel saturated with tap water and/or mild soap to remove the test material from the skin.

6.10 Initial Population/Final Population

An Initial Population confirming the amount of microorganism present will be performed prior to testing, and plated in duplicate. A Final Population will be performed to confirm the amount of microorganism present at the completion of the assay.

6.11 Incubation

The inoculated plates will be incubated at 30 °C \pm 2 °C for approximately 72 hours \pm 4 hours.

7.0 CALCULATIONS AND DATA HANDLING

Count colonies on plates that have between 25 and 250 colonies per plate. If no plates provide counts in that range, counts from those plates closest to that range will be used for analysis.

The microbial population recovered from each replicate of Test A, Test B, Test C, and Test D will be calculated as follows:

 Log_{10} Average Population = $log_{10}(C_i \times 10^{-D})$

Where:

 C_{i} Average of the plates counted

D Dilution Factor of the plates counted (for example, the dilution =factor is 0 for plating 1.0 mL aliquots and is -1 when plating 0.1

mL aliquots.)

NOTE: The reason that a log₁₀ transformation will be performed on the collected data is to obtain a linear scale. A linear scale, more appropriately a log₁₀ linear scale, is a basic requirement of the statistical models used in this study.

If colonies on one of the plates are uncountable, the count from the remaining plate will be used.

The raw data from sampling of all sites evaluated on a subject will be recorded on data collection forms.

8.0 **STATISTICS**

After calculating the log₁₀ populations recovered from Tests D, B, and A, these will be statistically compared to the Initial Population (Control) using a One-Way Analysis of Variance (ANOVA) with Dunnett Multiple Comparisons with the Control. All statistical calculations will be performed using the 0.05 level of significance for Type I (α) error.

Prior to comparing Phases to the Initial Population (Control), the 30-minute evaluation of the Initial Population should be shown to be statistically equivalent to the "time-zero" Initial Population of the microorganism. Hypotheses are:

 H_0 : Initial Population = Test Phase, or

 H_A : Initial Population \neq Test Phase.

If $p \le 0.05$ for each comparison to the control, H_0 will be rejected and the Test Phase will be considered to be significantly different from the Initial Population. There is potential for low variance of the data, which would result in rejecting H_0 . The difference between the Initial Population and the Test Phase will also be used to confirm significant differences. If the difference is greater than or equal to 0.20, the two tests will be determined to be significantly different. Differences less than 0.20 between the two tests will be determined to be not different.

The Product Efficacy Evaluation is effective if the antimicrobial test product produces a significant reduction in the population of the microorganism.

The Neutralizing/Recovery Medium Inhibition Evaluations are considered non-inhibitory if all recovered populations are not statistically different from the Initial Population of the microorganism.

The Diluent Broth Inhibition Evaluation is considered non-inhibitory if all recovered populations are not statistically different from the Initial Population of the microorganism.

Neutralization is considered adequate if all recovery populations are not statistically different from the Initial Population (with the exception of Test D). See table below for summary.

Neutralization Test/Phase	Required Results for Acceptance
Test Organism Viability/Initial Population –	30 minute sample cannot be statistically
Test C (IP)	different from 1 minute, or the evaluation
	fails.
Test Material Control/Product Efficacy –	Must be statistically different than Test C at
Test D (Phase I)	the within 1 minute and 30 minutes samples.
Neutralizer Toxicity Evaluation –	
Test B (Phase II)	
Diluent/Recovery Broth Toxicity Evaluation –	Cannot be statistically different at the within 1
Test B (Phase III)	minute or 30 minute samples.
Neutralization Effectiveness Evaluation –	
Test A (Phase IV)	

All values will be compared against the IP. The 30 minute evaluations of any test are used as a time representative to the longest possible wait time of a sample prior to being plated. A comparison will be performed against the FP to ensure the challenge suspension populations were consistent through testing.

The results and all source documents of the neutralization evaluation will be presented as an addenda in the Final Report.

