13.10 Data Handling

The estimated log₁₀ number of viable microorganisms per cm² recovered from each sample site will be designated the "R-value."

To convert the volumetric measure of the sample into the number of colony-forming units per square centimeter (cm²), the following formula will be employed:

$$R = \log_{10} \left[\frac{F\left(\frac{\sum c_i}{n}\right) 10^{-D}}{A} \right]$$

where:

R = the average colony-forming unit count in log_{10} scale per cm² of sampling surface

F = total number of mL of stripping fluid added to the sampling cylinder; in thisstudy, F = 6 mL for all samples

 $\frac{\sum c_i}{n}$ = average of the duplicate colony counts used for each sample collected

D =dilution factor of the plate counts

A = inside area of the cylinder in cm²; in this study, $A = 3.46 \text{ cm}^2$ (2.1 cm i.d.)

NOTE: The reason that a log₁₀ transformation will be performed on the collected data is to obtain a linear scale. A linear scale, more appropriately a log₁₀ linear scale, is a basic requirement of the statistical models used in this study.

If colonies on one of the plates are uncountable, the count from the remaining plate will be used. In order to avoid potential calculation problems due to taking the logarithm of zero, counts of zero will be considered 1 for further calculations.

Data collected from subjects with low test-day baseline counts on an anatomical test site ($< 3.11 \log_{10} \text{CFU/cm}^2$ from the skin of the abdomen, or $< 5.50 \log_{10} \text{CFU/cm}^2$ on the skin on the inguen) will not be used in the mITT Efficacy Analyses (Section 15.0).

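### Appendix 3 puts the un-neutralised kill control (Test D) into the pooled error that judges Tests A and B, and does not say whether p ≤ 0.05 or the 0.20 log10 rule decides (minor)

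*Combined protocol and SAP*

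**What the plan says.** - **Model.** Appendix 3, Section 8.0, says of the log10 populations "recovered from Tests D, B, and A, these will be statistically compared to the Initial Population", and gives the method: "using a One-Way Analysis of Variance (ANOVA) with Dunnett Multiple Comparisons with the Control". The test level is stated as "All statistical calculations will be performed using the 0.05 level of significance for Type I", and the alternative is two-sided.
- **Test D.** Appendix 3, Section 6.6, says this phase "determines whether the antimicrobial test material is able to reduce the population of the challenge microorganism". The inoculum goes into the test material and is plated on TSA without neutralizer. The acceptance table requires Test D to differ from the Initial Population (Test C). The text before the table exempts Test D from the not-different criterion, but nothing removes it from the ANOVA.
- **The 0.20 rule.** Section 8.0 warns "There is potential for low variance of the data", which could cause rejection of the null hypothesis, and adds a size criterion: "If the difference is greater than or equal to 0.20, the two tests will be determined to be significantly different". Anything smaller counts as no difference. It also describes this criterion as a confirmation of significant differences.
- **Zero counts.** Protocol Section 13.10 says "counts of zero will be considered 1 for further calculations", in the context of the clinical R-values. Appendix 3, Section 7.0, takes log10 of the average count for Tests A to D. It repeats the neighbouring rule of 13.10 on uncountable plates but not the zero rule.

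**The concern.** A one-way ANOVA with Dunnett comparisons uses one within-group variance for every comparison. The Initial Population and Tests A and B should all give counts in the countable range with similar scatter. Test D should give counts at or near zero. There, log10 values are either constant (complete kill, zeros set to 1) or very noisy (a few survivors). Equal variance therefore fails by design, and the standard error for A and B against the Initial Population depends on how the kill control happened to behave.

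The direction that matters is inflation. If an inflated error let a poor neutraliser pass, product carried over into the samples could go on killing after sampling. Post-treatment counts would be lowered, and the log10 reductions and responder rates raised. Protocol Section 10.0 makes this validation the safeguard against that.

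**Working it through.** The documents give no SD, power or sample-size figure for the neutralisation assay, so there is no stated figure to reproduce.

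**1. Inputs from the documents.** Four replicates per group (Tests B, C and D: four tubes; Test A: four subjects per product and species). Two-sided alpha 0.05. Size rule 0.20 log10. Inoculum titer about 3.0×10³ to 1.0×10⁴ CFU/mL, with 0.1 mL added to 5.0 mL.

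**2. Expected counts without kill.** 3.0×10³ × 0.1/5.1 = 58.8 and 1.0×10⁴ × 0.1/5.1 = 196.1 CFU/mL (log10 1.77 to 2.29). One-mL plates therefore fall within the 25 to 250 range for the Initial Population and Tests A and B. Test D is the exception.

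**3. Layout.** One species and one time point. Groups: Initial Population, Test B (sampling solution), Test B (diluent), and Test A for each of two products, which makes 5 groups. Adding Test D for each product makes 7.
- Without D: 4 comparisons, df = 5 × 3 = 15, Dunnett critical value 2.73.
- With D: 6 comparisons, df = 7 × 3 = 21, critical value 2.79.

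**4. Assumptions.** Replicate SD 0.10 log10 in the five non-D groups. Test D SD 0 (complete kill, zeros set to 1), 0.3 or 0.6.

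**5. Pooled error.** Pooled variance = (15 × 0.10² + 6 × SD_D²)/21 with D. SE of A minus C = pooled SD × √(2/4). Smallest significant difference = critical value × SE.

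| Model | Pooled SD | SE | Smallest significant difference |
|---|---|---|---|
| Without D | 0.100 | 0.071 | 0.19 |
| With D, SD 0 | √(0.15/21) = 0.085 | 0.060 | 0.17 |
| With D, SD 0.3 | √(0.69/21) = 0.181 | 0.128 | 0.36 |
| With D, SD 0.6 | √(2.31/21) = 0.332 | 0.235 | 0.65 |

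The true sampling SE of A minus C is 0.071 in every row. Only the estimate used in the test changes.

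**6. Chance of flagging a true 0.30 log10 loss in Test A.** Simulated, because the pooled SD itself varies from run to run.

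| Decision rule | Without D | D SD 0.3 | D SD 0.6 |
|---|---|---|---|
| p ≤ 0.05 alone | 92% | 33% | 3% |
| p ≤ 0.05 and ≥ 0.20 | 89% | 33% | 3% |
| ≥ 0.20 alone | 92% | 92% | 92% |

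The last row can be checked by hand: (0.30 − 0.20)/0.071 = 1.41, a normal probability of 0.92.

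**7. Complete kill, no true loss.** False flags per comparison by p alone rise from about 1.5% to 3.3%. With the 0.20 floor, none remain at replicate SD 0.05 and at most about 0.5% at SD 0.10, with or without D.

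**8. Sensitivity to survivor counts.** A second simulation used a mean of 100 colonies, replicate SD 0.05 on top of counting error, and a true 0.25 log10 loss. Requiring both p and 0.20, detection is 88% without D. With D it is 88% (complete kill), 88% (mean 0.5 surviving colonies), 71% (mean 2), 17% (median 5 with 0.3 log10 spread) and 2.6% (median 10 with 0.5 spread). Under the 0.20 rule alone it is about 88% throughout.

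**The case against.** The strongest reply is the 0.20 rule. Read literally, Section 8.0 classes every difference as different or not by its size alone, so no standard error enters the verdict and pooling Test D is harmless. A reader might infer from the pooled model that the adequacy verdict as a whole rests on a wrong standard error. The documents do not support that, because the literal rule would bypass the standard error. Nor do they rule out harm: the same paragraph presents 0.20 as a confirmation added because variance may be too low, and the acceptance criteria are all worded in terms of statistical difference. Both readings are open.

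A reader might also infer that complete kill, by shrinking the error, produces false failures. The 0.20 floor answers this, whichever reading applies. Complete kill also slightly improves detection: by p alone, from 92% to 96% for a 0.30 loss at SD 0.10.

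Third, near-uniform zeros are a natural expectation when 59 to 196 CFU/mL meet undiluted product and are plated without neutralizer. The severe figures need variable survivors, and their SD is assumed. That stands, and it limits the weight of the point.

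Last, a reader might say that complete kill cannot be analysed at all because log10 of zero is undefined. Section 13.10 of the same protocol already sets zeros to 1, so what is lacking is a cross-reference.

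**Conclusion.** The point holds in a limited form, as a minor one. As worded, the ANOVA takes Test D into the error term for A and B, and that error can be too small or too large depending on how completely the product kills. The verdict is affected in one combination only: p ≤ 0.05 is required together with a difference of at least 0.20, and Test D leaves few, variable survivors. Detection of a 0.30 log10 loss then falls from about 89% to 33% (Test D SD 0.3) or 3% (SD 0.6) at replicate SD 0.10, and an inadequate neutraliser could pass. If 0.20 alone decides, the miss rate is about 8% with or without Test D.

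The SDs and survivor counts are assumptions. The text does not exclude separate ANOVAs by species, product or time point. Those would change the degrees of freedom and the weight of Test D, but not the conclusion.

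**What to change.** In Appendix 3, Section 8.0:
- Fit the ANOVA and Dunnett comparisons to the Initial Population and Tests A and B only.
- Judge Test D separately against the Initial Population by its own log10 reduction.
- State whether p ≤ 0.05 and a difference of at least 0.20 are both required to declare a difference, or whether 0.20 alone decides.

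In Appendix 3, Section 7.0, apply the zero-to-1 rule of Section 13.10.

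The cost is a sentence or two, with no extra tests, replicates, subjects or data. Removing Test D without settling how p and 0.20 combine would leave the acceptance rule ambiguous, so both belong in the same edit.
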